F1419	Cocaine abuse with unspecified cocaine-induced disorder.
F1510	Other stimulant abuse, uncomplicated.
F15120	Other stimulant abuse with intoxication, uncomplicated.
F15121	Other stimulant abuse with intoxication delirium.
E15122	Other stimulant abuse with intoxication with perceptual
F13122	disturbance.
F15129	Other stimulant abuse with intoxication, unspecified.
F1514	Other stimulant abuse with stimulant-induced mood disorder.
E15150	Other stimulant abuse with stimulant-induced psychotic
113130	disorder with delusions.
F15151	Other stimulant abuse with stimulant-induced psychotic
113131	disorder with hallucinations.
F15159	Other stimulant abuse with stimulant-induced psychotic
115157	disorder, unspecified.
F15180	Other stimulant abuse with stimulant-induced anxiety disorder.
F15181	Other stimulant abuse with stimulant-induced sexual
	dysfunction.
F15182	Other stimulant abuse with stimulant-induced sleep disorder.
F15188	Other stimulant abuse with other stimulant-induced disorder.
F1519	Other stimulant abuse with unspecified stimulant-induced
	disorder.

Hallucinogens:	
F1610	Hallucinogen abuse, uncomplicated.
F16120	Hallucinogen abuse with intoxication, uncomplicated.
F16121	Hallucinogen abuse with intoxication with delirium.
F16122	Hallucinogen abuse with intoxication with perceptual disturbance.
F16129	Hallucinogen abuse with intoxication, unspecified.
F1614	Hallucinogen abuse with hallucinogen-induced mood disorder.
F16150	Hallucinogen abuse with hallucinogen-induced psychotic disorder with delusions.

Hallucinogens:	
F16151	Hallucinogen abuse with hallucinogen-induced psychotic
	disorder with hallucinations.
F16159	Hallucinogen abuse with hallucinogen-induced psychotic
	disorder, unspecified.
F16180	Hallucinogen abuse with hallucinogen-induced anxiety
	disorder.
F16183	Hallucinogen abuse with hallucinogen persisting perception
	disorder (flashbacks).
F16188	Hallucinogen abuse with other hallucinogen-induced disorder.
F1619	Hallucinogen abuse with unspecified hallucinogen-induced
	disorder.

Inhalants:	
F1810	Inhalant abuse, uncomplicated.
F18120	Inhalant abuse with intoxication, uncomplicated.
F18121	Inhalant abuse with intoxication delirium.
F18129	Inhalant abuse with intoxication, unspecified
F1814	Inhalant abuse with inhalant-induced mood disorder.
F18150	Inhalant abuse with inhalant-induced psychotic disorder with
	delusions.
F18151	Inhalant abuse with inhalant-induced psychotic disorder with
	hallucinations.
F18159	Inhalant abuse with inhalant-induced psychotic disorder,
	unspecified.
F1817	Inhalant abuse with inhalant-induced dementia.
F18180	Inhalant abuse with inhalant-induced anxiety disorder.
F18188	Inhalant abuse with other inhalant-induced disorder.
F1819	Inhalant abuse with unspecified inhalant-induced disorder

Other Psychoactive Substances:	
F1910	Other psychoactive substance abuse, uncomplicated.
F19120	Other psychoactive substance abuse with intoxication, uncomplicated.
F19121	Other psychoactive substance abuse with intoxication delirium.
F19122	Other psychoactive substance abuse with intoxication with perceptual disturbances.
F19129	Other psychoactive substance abuse with intoxication, unspecified.
F1914	Other psychoactive substance abuse with psychoactive substance-induced mood disorder.
F19150	Other psychoactive substance abuse with psychoactive substance-induced psychotic disorder with delusions.
F19151	Other psychoactive substance abuse with psychoactive substance-induced psychotic disorder with hallucinations.
F19159	Other psychoactive substance abuse with psychoactive substance-induced psychotic disorder, unspecified.
F1916	Other psychoactive substance abuse with psychoactive substance-induced persisting amnestic disorder.

Other Psychoactive Substances:	
F1917	Other psychoactive substance abuse with psychoactive
	substance-induced persisting dementia.
F19180	Other psychoactive substance abuse with psychoactive
	substance-induced anxiety disorder.
F19181	Other psychoactive substance abuse with psychoactive
	substance-induced sexual dysfunction.
F19182	Other psychoactive substance abuse with psychoactive
	substance-induced sleep disorder.
F19188	Other psychoactive substance abuse with other psychoactive
	substance-induced disorder.

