Re-presentation to	To assess the clinical	NACRS (ICES)	Baseline; 12 months
any Emergency	impact of the		
Department in	provision of a		
Ontario for Self-harm	smartphone-assisted		

Table 2. Outcome Measures

	PST service.		
Re-presentation to any Emergency Department for any reason	To assess the clinical impact of the provision of a smartphone-assisted PST service.	NACRS (ICES)	Baseline; 12 months
Admission to any hospital in Ontario for any reason	To assess the clinical impact of the provision of a smartphone-assisted PST service.	NACRS (ICES)	Baseline; 12 months
Hospital outpatient appointments in Ontario for any reason	To assess the clinical impact of the provision of a smartphone-assisted PST service.	OHIP (ICES)	Baseline; 12 months
Primary care appointments	To assess the clinical impact of the provision of a smartphone-assisted PST service.	OHIP (ICES)	Baseline; 12 months
Mortality for reasons other than suicide	To assess the clinical impact of the provision of a smartphone-assisted PST service.	ORGD (ICES)	Baseline; 12 months
Total Health Care Costs	To assess the economic impact of the provision of a smartphone-assisted PST service.	OHIP, DAD, NACRS, NRS, CCRS, OMHRS, ODB, ADP (ICES)	Baseline; 12 months
Physician Health Care Costs	To assess the economic impact of the provision of a smartphone-assisted PST service.	OHIP (ICES)	Baseline; 12 months
Emergency Department Health Care Costs	To assess the economic impact of the provision of a smartphone-assisted PST service.	NACRS (ICES)	Baseline; 12 months
Hospitalization Health Care Costs	To assess the economic impact of the provision of a smartphone-assisted PST service.	DAD (ICES)	Baseline; 12 months
Other Health Care Costs	To assess the economic impact of the provision of a	NRS, CCRS, OMHRS, ODB, ADP (ICES)	Baseline; 12 months

	smartphone-assisted		
	PST service.		
Prognostic outcome n	neasures		
Age	To assess differences	RPDB (ICES)	Baseline
	between subgroups.		
Previous	To assess differences	NACRS (ICES)	Baseline
hospitalization for	between subgroups.		
self-harm			
Previous	To assess differences	NACRS (ICES)*	Baseline
hospitalization for	between subgroups.		
substance use			

* Appendix B for list of ICD-10-CM codes.

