4.3.3. Statistical Methods

Outcomes

The unit of analysis will be the individual patient. To evaluate the effectiveness of the complex intervention at population-level (primary trial analysis), all outcomes will be obtained from ICES, regardless of whether men received or participated in the study therapy. Dichotomous primary and secondary outcomes will be described, by arm, using frequencies and percentages. The primary composite outcome as well as its individual components (completed suicides and re-presentations within 1 year) will be compared between the intervention and control sites using generalized linear mixed effects regression, accounting for the pre-and post-intervention measures using repeated cross-sectional analysis [51]. Differences between the arms will be expressed as absolute and relative differences in proportions, together with 95% confidence intervals. Models will account for clustering at the Emergency Department level and over time using random effects. Cluster level covariates for factors used in the allocation procedure, namely urban/rural, onsite psychiatric service, and size will be included in regression models. Additional analyses will adjust for individual prognostic variables including age, ethnicity, pre-specified comorbidities (such as previous hospitalizations for substance use), and repeat as compared with first-time presentations for self-harm.

All binary secondary outcomes (representation to the ED for any reason, admission to hospital for any reason, and mortality for any reason) will be analyzed as described for the primary outcome. Length of hospital stay for any reason, number of hospital outpatient appointments, number of primary care appointments and cost data will be analyzed as described for the primary outcome, that is, using generalized linear mixed effects regression, but with either the Poisson or negative binomial distribution and using the log link function. Differences between the arms will be expressed as rate ratios together with 95% confidence intervals.

Additional subgroup analyses will be carried out for the following subgroups: first time presentations of self-harm compared to repeat presentations; Francophone versus Anglophone; men with substance abuse disorders versus no substance abuse disorder; and rural versus urban residence.

Health Economic Evaluation

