6.3. List of Substance Abuse ICD-10-CM Codes Included in Data Collection

Code	Description
Alcohol:	
F1010	Alcohol abuse, uncomplicated.
F10120	Alcohol abuse with intoxication, uncomplicated.
F10121	Alcohol abuse with intoxication delirium.
F10129	Alcohol abuse with intoxication, unspecified.
F1014	Alcohol abuse with alcohol-induced mood disorder.
F10150	Alcohol abuse with alcohol-induced psychotic disorder with
	delusions.
F10151	Alcohol abuse with alcohol-induced psychotic disorder with
1 10131	hallucinations.
F10159	Alcohol abuse with alcohol-induced psychotic disorder,
	unspecified.
Alcohol:	
F10180	Alcohol abuse with alcohol-induced anxiety disorder.
F10181	Alcohol abuse with alcohol-induced sexual dysfunction.
F10182	Alcohol abuse with alcohol-induced sleep disorder.
F10188	Alcohol abuse with other alcohol-induced disorder
F1019	Alcohol abuse with unspecified alcohol-induced disorder.

Opioids:	
F1110	Opioid abuse, uncomplicated.
F11120	Opioid abuse with intoxication, uncomplicated.
F11121	Opioid abuse with intoxication delirium.
F11122	Opioid abuse with intoxication with perceptual disturbance.

F11129	Opioid abuse with intoxication, unspecified.
F1114	Opioid abuse with opioid-induced mood disorder.
E11150	Opioid abuse with opioid-induced psychotic disorder with
F11150	delusions.
E11151	Opioid abuse with opioid-induced psychotic disorder with
111131	hallucinations.
F11150	Opioid abuse with opioid-induced psychotic disorder,
111137	unspecified.
F11181	Opioid abuse with opioid-induced sexual dysfunction.
F11182	Opioid abuse with opioid-induced sleep disorder.
F11188	Opioid abuse with other opioid-induced disorder.
F1119	Opioid abuse with unspecified opioid-induced disorder.
Cannabis:	
F12120	Cannabis abuse with intoxication, uncomplicated.
F12121	Cannabis abuse with intoxication delirium.
F12122	Cannabis abuse with intoxication with perceptual disturbance.
F12129	Cannabis abuse with intoxication, unspecified.
F12150	Cannabis abuse with psychotic disorder with delusions.
F12151	Cannabis abuse with psychotic disorder with hallucinations.
F12159	Cannabis abuse with psychotic disorder, unspecified.
F12180	Cannabis abuse with cannabis-induced anxiety disorder.
F12188	Cannabis abuse with other cannabis-induced disorder.
F1219	Cannabis abuse with unspecified cannabis-induced disorder.
C. J. C.	
Sedatives:	Sodativo humantio an anvialatio abuse un complicated
Sedatives: F1310	Sedative, hypnotic or anxiolytic abuse, uncomplicated.

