Sedatives: F1310 F13120 F13121 F13129 F13129 F1314 F13150 F13151 F13159 F13180 F13182 F13188	Sedative, hypnotic or anxiolytic abuse, uncomplicated. Sedative, hypnotic or anxiolytic abuse with intoxication, uncomplicated. Sedative, hypnotic or anxiolytic abuse with intoxication delirium. Sedative, hypnotic or anxiolytic abuse with intoxication, unspecified. Sedative, hypnotic or anxiolytic abuse with sedative, hypnotic or anxiolytic-induced mood disorder. Sedative, hypnotic or anxiolytic abuse with sedative, hypnotic or anxiolytic-induced psychotic disorder with delusions. Sedative, hypnotic or anxiolytic abuse with sedative, hypnotic or anxiolytic-induced psychotic disorder with hallucinations. Sedative, hypnotic or anxiolytic abuse with sedative, hypnotic or anxiolytic-induced psychotic disorder with hallucinations. Sedative, hypnotic or anxiolytic abuse with sedative, hypnotic or anxiolytic-induced psychotic disorder, unspecified. Sedative, hypnotic or anxiolytic abuse with sedative, hypnotic or anxiolytic-induced anxiety disorder. Sedative, hypnotic or anxiolytic abuse with sedative, hypnotic or anxiolytic-induced sexual dysfunction. Sedative, hypnotic or anxiolytic abuse with sedative, hypnotic or anxiolytic-induced sexual dysfunction. Sedative, hypnotic or anxiolytic abuse with sedative, hypnotic or anxiolytic-induced sleep disorder. Sedative, hypnotic or anxiolytic abuse with other sedative, hypnotic or anxiolytic-induced disorder. Sedative, hypnotic or anxiolytic abuse with other sedative, hypnotic or anxiolytic-induced disorder.

Study Protocol Version 1, Date: December 1, 2017 Page 44 of 51

Stimulants:	
F1410	Cocaine abuse, uncomplicated.
F14120	Cocaine abuse with intoxication, uncomplicated.
F14121	Cocaine abuse with intoxication with delirium.
F14122	Cocaine abuse with intoxication with perceptual disturbance.
F14129	Cocaine abuse with intoxication, unspecified.
F1414	Cocaine abuse with cocaine-induced mood disorder.
E14150	Cocaine abuse with cocaine-induced psychotic disorder with
F14150	delusions.
E14151	Cocaine abuse with cocaine-induced psychotic disorder with
F14151	hallucinations.
E14150	Cocaine abuse with cocaine-induced psychotic disorder,
F14139	unspecified.
F14180	Cocaine abuse with cocaine-induced anxiety disorder.
F14181	Cocaine abuse with cocaine-induced sexual dysfunction.
F14182	Cocaine abuse with cocaine-induced sleep disorder.
F14188	Cocaine abuse with other cocaine-induced disorder.

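### The substance-abuse code list in Section 6.3 has an uncomplicated-abuse code for every class except cannabis, so men with only that record count as having no substance abuse

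*Protocol*

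**What the plan says.** Section 6.3 sets out, class by class, the substance-abuse codes to be collected. Most classes open with the plain code for abuse without complication: "Alcohol abuse, uncomplicated" (F1010), "Opioid abuse, uncomplicated" (F1110), "Sedative, hypnotic or anxiolytic abuse, uncomplicated" (F1310), "Cocaine abuse, uncomplicated" (F1410), "Hallucinogen abuse, uncomplicated" (F1610), with matching rows for other stimulants (F1510), inhalants (F1810) and other psychoactive substances (F1910). The cannabis class opens with F12120, "Cannabis abuse with intoxication, uncomplicated".

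Table 2 in Section 4.1.4 names earlier hospitalization for substance use as a prognostic variable, taken from NACRS and collected to look at differences between subgroups. Its footnote reads "Appendix B for list of ICD-10-CM codes". Appendix B is Section 6.2, the self-harm list. The substance list is Section 6.3, which has no appendix letter.

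Section 4.3.3 uses earlier substance-use hospitalization as an example of the comorbidities in the additional adjusted analyses. It also names a subgroup comparison of "men with substance abuse disorders versus no substance abuse disorder".

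**The concern.** The list treats the same kind of record differently by substance. A man whose only earlier record is uncomplicated inhalant or cocaine abuse is counted as a substance-abuse case. A man whose only earlier record is uncomplicated cannabis abuse is not. The protocol gives no reason for the difference, and nothing in it suggests that simple abuse was meant to be excluded for one substance alone.

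The covariate in the additional adjusted analyses would therefore carry some misclassification. If the subgroup is built from the same list, true cases would also sit in its comparison group and could blur the contrast.

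The timing matters. Section 5.5 says the cohorts are created at ICES Central and then sent to Ottawa for analysis. A code left off the list may therefore be missing from the analysts' data and hard to recover later.

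**Working it through.** The protocol states no figure on this point, so there is none to reproduce. The check is a comparison of code families, followed by an illustration of size on assumed inputs.

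**Step 1: tabulate Section 6.3.**

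| Family | Codes legible | Uncomplicated abuse (ending 10) | Unspecified disorder (ending 19) |
|---|---|---|---|
| F10 alcohol | 13 | yes | yes |
| F11 opioids | 13 | yes | yes |
| F12 cannabis | 10 | **no** | yes |
| F13 sedatives | 12 | yes | **not seen** |
| F14 cocaine | 14 | yes | yes |
| F15 other stimulants | 14 | yes | yes |
| F16 hallucinogens | 13 | yes | yes |
| F18 inhalants | 12 | yes | yes |
| F19 other psychoactive | 15 | yes | **not seen** |

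The uncomplicated-abuse code appears in 8 of 9 families and is absent only in F12. The number F1210 is inferred from the pattern of the other families; the protocol does not print it.

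**Step 2: apply the rule.** Take a man with one earlier record. Uncomplicated alcohol abuse (F1010) is listed, so he is a case. Uncomplicated cannabis abuse is not listed, so he is not. A man with uncomplicated cannabis abuse and any other listed code is still captured. The error is confined to men with no other listed code.

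**Step 3: trace the uses.** Section 4.3.3 adjusts the main models for cluster-level allocation factors. Substance use enters only the additional adjusted analyses and, by inference, one additional subgroup analysis. The sample size calculation in Section 4.1.5 does not use it.

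**Step 4: illustrate the size.** Let p be the true share of men with substance abuse, and q the share of those men identifiable only by the missing code. The protocol gives neither. The share of true cases in the no-substance-abuse group is

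c = pq / (1 − p + pq).

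Assume p = 20% to 45% and q = 2% to 20%. The upper p borrows the alcohol-misuse figure for men in the U.K. study cited in Section 3.1.1, which is a different quantity. The range for q is a pure assumption.

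- Low end: 0.20 × 0.02 = 0.004; c = 0.004 / (0.80 + 0.004) = 0.5%.
- High end: 0.45 × 0.20 = 0.09; c = 0.09 / (0.55 + 0.09) = 14.1%.

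On 2,000 men this is 2,000 × 0.004 = 8 to 2,000 × 0.09 = 180 men. If cannabis-only men respond like other men with substance abuse, an absolute difference between subgroup effects would keep 1 − c of its size, that is 99.5% to 85.9%. The width of the range shows that the size is not known.

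**Step 5: the footnote, taken separately.** Section 4.1.4 sends the reader to Appendix A for the self-harm codes, but Appendix A (Section 6.1) is the site list. Table 2 sends the reader to Appendix B for the substance codes, but Appendix B is the self-harm list. Both pointers are one letter early. This slip has no bearing on the cannabis row.

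**The case against.** The strongest objection is that the row may have been lost in the machine-read text and not in the protocol. The text near the cannabis block is damaged: some opioid codes just above are misread, and the sedative rows below are garbled and repeated. F1319 and F1919 are not seen either. So either rows have dropped out at class boundaries, or the list was never uniform. The blocks differ in other ways too; cannabis, for example, has no mood-disorder row. This lowers certainty, and it is why the source table should be checked first. It does not remove the point, because the ten cannabis rows themselves read cleanly from the class header to F1219.

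The limited reach is also a fair objection, and it stands. Only additional analyses are touched, and only men with no other listed code.

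A reader might infer more than the protocol supports in three ways:

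- **That the Table 2 footnote would make the variable a copy of self-harm history.** The parallel one-letter slip in Section 4.1.4 and the explicit title of Section 6.3 show a clerical error that an analyst would not follow literally.
- **That the subgroup is certainly misclassified.** Section 4.3.3 does not say which codes define it. The link rests on Table 2's stated purpose and the title of the list.
- **That a definite share of the comparison group is contaminated, or that the contrast must shrink.** The inputs are assumed, and shrinkage also requires that effects differ between the subgroups and that cannabis-only men respond like the other cases.

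**Conclusion.** The point holds as a small defect in a stated rule. As the list reads, men whose only substance record is uncomplicated cannabis abuse are classed as having no substance abuse. This affects the additional covariate-adjusted analyses and, if the subgroup uses the Section 6.3 list, the substance-abuse subgroup. The size is unknown; the range in the working is illustrative and should not be quoted as an estimate. The primary outcome, the primary model and the power are unaffected. The conclusion assumes that the absent row is absent from the protocol itself, which a look at the source table will settle. The wrong appendix letter is a separate clerical matter.

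**What to change.** Before the ICES extraction:

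1. Check the cannabis block of Section 6.3 against the source table. If the row is absent there, add the uncomplicated cannabis abuse code (F1210), or state why it is left out.
2. In the same check, see whether the closing unspecified-disorder rows for sedatives (F1319) and other psychoactive substances (F1919) are also absent, and settle each one.
3. State in Section 4.3.3 whether the substance-abuse subgroup is defined by the Section 6.3 list.
4. As a clerical correction, point the Table 2 footnote to Section 6.3.

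The cost is a short check, up to three added code rows, one sentence and one cross-reference. Made before extraction, the change needs no new data source and leaves the sample size and primary analysis as they are.
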